2.8 ASSESSMENTS AND QUESTIONNAIRES

1) The following measures are collected during the **Baseline Screening Visit** and again during the **Outcome Assessments (post intervention and at 6 months follow-up):**

Self-harm measures

Administered by researcher:

- a) Self-harm frequency over the past 3 months: Using the timeline follow-back technique (TLFB, Sobell & Sobell, 2008). This is an interview method conducted by the researcher who reconstructs together with the participant the number of self-harm behaviours using calendar cues. It has been successfully used in previous self-harm research including our proof-of-concept study ([name] et al., 2020; Maschauer et al., in preparation).
- b) Self-harm severity over the past 3 months: A combined measure of a Visual Analogue Scale, severity criteria used in the NSSI disorder in the Diagnostic and Statistical Manual of Mental Disorder Fifth Edition (DSM-V, 39) and the number of different self-harm methods used (also termed self-harm versatility), elicited via these open questions: "In the last three months, how severe was the worst injury that you inflicted to yourself? Can you list all the ways that you have used to harm yourself in the last three months?" This method was advised by the YPAG to avoid scales listing numerous self-harm methods which could be triggering/enabling.
- c) **Mental imagery related to self-harm:** Using the *Self-Harm Imagery Interview* adapted from (Hales et al., 2011): This interview is about mental images that deal with self-harm or occur with self-harm. It asks participants to think about one of these and explores their thoughts and emotions in relation to the image.
- d) Suicidal thoughts and behaviour: Using the *Columbia-Suicide Severity Rating Scale* (C-SSRS) (Posner et al., 2011) is widely used interview for suicide risk assessment and

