measurement of suicidal ideation and behaviour. The *Lifetime/Recent* version will be used at screening to gather recent history of suicidality including suicidal ideation and/or behaviour. The scale measures four constructs: severity of ideation on a 5-point ordinal scale (from 1=wish to be dead, to 5=suicidal intent with plan); intensity of ideation via 5 items (e.g. frequency, duration etc.), each rated on a 5-point ordinal scale; behavior rated on a nominal scale (including actual, aborted, and interrupted attempts, preparatory behavior and non-suicidal self-injurious behavior); and lethality rated on a 6-point ordinal scale. **This measure will additionally be used at the start of each face-to-face FIT session.**

e) Motivation to reduce self-harm: Using the State Motivation for Reducing Self-harm (SM-SH) scale (Parham et al., 2017). This scale measures participants' motivation to control their self-harm using 12 items that measure the strength of their motivational cognitions in the present moment, rated on a 10-point likert scale, from 0 (never) to 10 (constantly).

Self-report:

f) Urge to self-harm: Using the Craving Experience Questionnaire for Self-Harm (CEQ-SH), adapted from CEQ (May et al., 2014) This questionnaire assesses the urge to self-harm and assesses frequency, intensity, salience or dismissability of intrusive thoughts surrounding self-harm. It is rated on a 10 point Likert type scale ranging from not at all (0) to constantly (10).

Clinical and functional measures

Self-report:

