- a) Symptoms of low mood and anxiety: using 1) the Revised Children's Anxiety and Depression Scale (RCADS) for 12 17 year olds, is a 47 item youth self report questionnaire with six subscales (separation anxiety disorder, social phobia, generalised anxiety disorder, panic disorder, obsessive compulsive disorder, and low mood (major depressive disorder)) and a total anxiety scale and total internalising scale. The RCADS has good internal consistency, test-retrest reliability and convergent validity. 2) the Depression, Anxiety and Stress Scale (DASS-21) (Antony et al., 1998), for 18 25 year olds, a 21-item scale measuring levels of depression, anxiety and stress over the past week. It has acceptable to excellent internal consistency validated in both clinical and non-clinical samples. The depression scale measures symptoms associated with dysphoric mood e.g. worthlessness; the anxiety scale measures symptoms associated with physiological arousal such as trembling, as opposed to symptoms of generalised anxiety; and the stress scale measures symptoms of tension and reactivity to stressful events;
- b) **Psychological wellbeing:** using the Warwick-Edinburgh Mental Well-being Scale (WEMWBS) (Tennant et al., 2007), which consists of 14 positively worded items. Items are rated on a 5 point likert scale ranging between none of the time (1) and all of the time (5) with five

response categories and assesses mental wellbeing covering both hedonic and eudemonic perspectives.

- c) **Emotion regulation abilities:** using the *Difficulties in Emotion Regulation Scale-Short Form* (Kaufman et al., 2016), an 18-item scale adapted from the original long version that measures general emotion regulation ability as well as various aspects of emotion regulation (in six subscales), e.g. difficulties engaging in goal directed behaviour when upset, and limited access to emotion regulation strategies. The scale has high internal consistency.
- d) **Engagement in other risky, self-destructive behaviours** (e.g., binge eating, substance misuse): using the *11-item behaviour supplement to the Borderline Symptom List* (Bohus et al., 2001). The scale has high internal validity and test-retest reliability.

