2.9 DATA ANALYSIS

Sample Size

We aim to reach N=15 participants who will complete treatment and 6 months follow-up assessments. Based on an expected 25% attrition rate from our previous study ([name] et al., 2020), N=20 participants will be enrolled in the study.

Statistical Analysis

Quantitative data will be summarised into descriptive statistics such as means, medians, inter quartile range, standard deviations for all measures and percentage change and Cohen's *d* for the clinical outcomes repeated at pre- and post-intervention. Qualitative data will be analysed using a co-produced thematic analysis approach based on Braun & Clarke (2006) and Dewa et al. (2021a, 2021b). Data and all appropriate documentation will be stored for a minimum of 10 years after the completion of the study, including the follow-up period.

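### Percentage change on the WEMWBS total depends on how its items are coded, so section 2.9 should keep that measure for outcomes with a true zero

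*Combined protocol and SAP*

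**What the plan says.** Under Statistical Analysis, section 2.9 lists means and medians together with "inter quartile range, standard deviations for all measures and percentage change and Cohen's" d. The percentage change and d are "for the clinical outcomes repeated at pre- and post-intervention". The section does not say which of those outcomes receive a percentage, whether it is taken from group means or averaged over participants, or from what scale origin it is measured.

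Section 2.8 places the WEMWBS under clinical and functional measures, collected at baseline and at both outcome assessments. It is a scale "which consists of 14 positively worded items", answered on a "5 point likert scale ranging between none of the time (1) and all of the time (5"). Wellbeing is a named secondary objective in section 2.3.

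Other repeated measures have a different origin. Self-harm frequency is a count: the researcher "reconstructs together with the participant the number of self-harm behaviours using calendar cues". In the same section the urge and motivation scales are described with items that start at 0.

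**The concern.** A percentage change divides by the baseline value, so it has meaning only if zero on the scale means none of the quantity. On the WEMWBS, a participant who gives the lowest answer to every item still scores 14. Those 14 points come from the numbers attached to the answer boxes, yet they enter the denominator for every participant. Someone who coded the same boxes 0 to 4 would report a different percentage from identical answers.

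What is at stake is how the secondary results read. A table with percentage change in self-harm episodes in one row and percentage change in WEMWBS in the next invites a comparison that the second figure cannot support.

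**Working it through.** **Inputs.** From section 2.8: 14 items, lowest answer 1, highest answer 5. From section 2.9: percentage change planned for the repeated clinical outcomes. The documents give no WEMWBS baseline and no expected change, so the baselines and the 7-point gain (half a point per item) below are assumptions. I also assume that items are summed. If the item mean is used instead, every ratio below is the same.

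**The plan's own figure.** The only calculation in section 2.9 is the sample size: 15/(1 − 0.25) = 20, which reproduces. It does not bear on this point.

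**Range.** 14 × 1 = 14 to 14 × 5 = 70, a span of 56. Coded 0 to 4, the same answers run from 0 to 56.

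**Formulas.** Let B be the baseline total on the 1-to-5 coding and D the change.
- Percentage on the 1-to-5 coding: D/B
- Percentage on the 0-to-4 coding: D/(B − 14)
- Ratio of the second to the first: B/(B − 14)
- Relative amount by which the first is lower: 14/B, whatever the size or sign of D

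**Results for a gain of 7 points.**

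| Assumed B | 7/B | 7/(B − 14) | B/(B − 14) | 14/B |
|---|---|---|---|---|
| 21 | 33.3% | 100.0% | 3.00 | 66.7% |
| 28 | 25.0% | 50.0% | 2.00 | 50.0% |
| 35 | 20.0% | 33.3% | 1.67 | 40.0% |
| 42 | 16.7% | 25.0% | 1.50 | 33.3% |
| 49 | 14.3% | 20.0% | 1.40 | 28.6% |
| 56 | 12.5% | 16.7% | 1.33 | 25.0% |

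**What holds without an assumed baseline.** B cannot exceed 70, so 14/B is never below 14/70 = 20%. At B = 14 the 0-to-4 percentage is undefined. The largest possible fall, from 70 to 14, reads as 56/70 = 80% on the 1-to-5 coding and 56/56 = 100% on the other. A self-harm count can fall by 100%.

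**Averaging.** If percentages are calculated per participant and then averaged, each participant carries their own factor B/(B − 14), and those with the lowest baselines are affected most.

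**Cohen's d.** Subtracting 14 from every score leaves both the mean difference and the standard deviations unchanged, so d is unchanged. A numerical check on 15 simulated pairs gave 0.729 under both codings when standardised by the baseline SD, and 0.598 under both when standardised by the SD of the changes.

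**The case against.** The strongest reply is that percentage change does not stand alone. The same sentence plans Cohen's d, which is free of the origin, and means and standard deviations for every measure. A reader will have an origin-free effect size beside each percentage and can largely read the mean change from the tabulated means. The match is exact only if both means are taken in the same participants, and with 25% attrition expected they need not be. This reply stands: a reader might infer that percentage change is the plan's sole effect measure for the scales, and section 2.9 does not support that.

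A second reply is that little depends on the figure. This is a descriptive series of 20 whose primary objective is feasibility, acceptability and safety, and no test, decision rule or sample size uses percentage change. A reader might go further and infer that the percentages could steer the choice of outcome for a later randomised trial. Nothing in the documents says that outcomes will be chosen by ranking percentages, so that is conjecture.

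A third reply concerns scope. The WEMWBS is the only repeated clinical or functional scale for which section 2.8 states that items start at 1; it gives no item origin for RCADS, DASS-21, DERS-SF, AUDIT, CUDIT-R, ASA or TEPS. The contrast with the zero-based urge scale is also uncertain, because section 2.4 lists urge under mechanisms and it may not count as a clinical outcome for section 2.9. Both limits are right. The contrast with self-harm counts is enough to carry the point.

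None of these replies makes the WEMWBS percentage interpretable. It would still be one of only two change measures that the plan names.

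**Conclusion.** The point holds as a minor reporting correction. Followed as written, section 2.9 produces a WEMWBS percentage that is set partly by item coding and is not comparable with percentage change in self-harm counts. Relative to a 0-to-4 coding, the 1-to-5 figure is lower by 14/B: at least 20% at any possible baseline, and 33% to 50% on the assumption that the baseline total lies between 42 and 28.

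It is tempting to read this as the plan understating change by a third to a half. The documents do not support that, for two reasons. The range depends on a baseline that they do not give; over baselines from 21 to 70 it runs from 67% down to 20%. And setting the lowest possible score to zero is itself a convention. Measured against a third convention, the share of the possible range, a 7-point gain is 7/56 = 12.5% at every baseline, and the raw 25%, 20% and 16.7% at baselines of 28, 35 and 42 would look too large. The defect is arbitrariness, with no known direction or size of bias.

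The primary endpoints, the sample size and the planned Cohen's d are unaffected.

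**What to change.** In section 2.9:

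- Restrict percentage change to outcomes with a true zero, such as self-harm episode counts and, where a pre-intervention count is available, emergency department visits. State whether it is calculated from group totals or averaged over participants; group totals avoid dividing by zero for a participant with none at baseline.
- For the WEMWBS and the other summed questionnaire scales, report the mean paired change in scale points among participants with both assessments, together with the Cohen's d already planned. Scales whose items start at 0 belong here too, since their zero is only the lowest answer.
- Change as a share of the possible range (for the WEMWBS, change/56) may be added, but is optional.

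The cost is a sentence or so of text and trivial analysis work, with no new data. The one loss is a familiar summary for the questionnaire scales.

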Our first proof-of-concept study compared IMAGINATOR (for brevity, we will refer to FIT plus the IMAGINATOR app as "IMAGINATOR") with treatment as usual in 38 YP aged 16-25 years old, and showed a medium-to-large effect size (d = 0.65-0.75 [CI: 0.3–16.1]) reduction of self-harm over 6 months following IMAGINATOR ([name] et al., 2020). Eighty-two % of participants said they would recommend the intervention to a friend. No adverse events were reported. Qualitative feedback highlighted that YP valued the focus on developing goals, positive emotions and motivational tools rather than unpacking negative cognitions (Maschauer et al., in prep). Mental imagery was also valued as a coping strategy that was easy to apply whilst maintaining privacy ("I can do it anywhere and nobody knows I am doing it") (Maschauer et al., in prep).

This work suggests that IMAGINATOR could be feasible, acceptable and helpful at reducing selfharm in YP with a potential for reaching those who often fall in the gap of current provision.

Need for Improvement, Re-design and Adaptation of IMAGINATOR

Evidence from the literature, our proof-of-concept study, working with NHS clinicians and with our Young Person's Advisory Group (YPAG) has since highlighted several limitations of the current IMAGINATOR intervention and the need for improvement.

Clinicians from NHS Children and Adolescent Mental Health Services (CAMHS) via workshops and presentations suggested that IMAGINATOR should be extended and made available to younger teenagers too (e.g. from age 12), as self-harm tends to start earlier than 16 years old and IMAGINATOR could hold promise in particular as an early intervention. Our YPAG agreed with this need and indicated that IMAGINATOR can be suitable for YP across the teenage-young adult age range, but provided that users can choose between a few different options of the app's look and modules to use. This reflects previous literature (Hetrick et al., 2020) suggesting the need for user segmentation around how an app feels, and modality of usage such as data tracking or gamification. YP also report that triggers and self-help strategies are often idiosyncratic (Gillies et al., 2018) further highlighting the importance of personalisation and the need to increase this drastically in the IMAGINATOR app.

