Building on our proof-of-concept study, there is therefore a need for a further adaptation and development stage of the IMAGINATOR intervention before its efficacy can be tested in a randomised controlled trial. In particular, there is a need for:

- An iOS version of the app
- A new app design and functionalities to include a degree of personalisation, segmentation, inclusivity and modularity
- Tailoring the intervention to better serve the needs of minoritised YP
- Adapting the intervention to younger teenagers.

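### Pre-post change is summarised as Cohen's d in 15 to 20 participants, and fewer for the age-specific mood scales; Hedges' g with one named denominator would remove a small bias away from zero

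*Combined protocol and SAP*

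**What the plan says.** Section 2.9 plans descriptive statistics for all measures (means, medians, interquartile ranges, standard deviations) and adds "percentage change and Cohen's *d* for the clinical outcomes repeated at pre- and post-intervention". This is the only standardised effect measure in the plan. The section does not name the denominator for paired data, a small-sample correction, a confidence interval, or the n to be shown with each value.

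On sample size the same section says "We aim to reach N=15 participants who will complete treatment and 6 months follow-up assessments". It then allows for 25% attrition, a figure taken from the team's earlier study, and sets enrolment: "N=20 participants will be enrolled in the study".

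Section 2.8 measures low mood and anxiety with two instruments chosen by age: "Anxiety and Depression Scale (RCADS) for 12 17 year olds" and, in DASS-21, one "for 18 25 year olds, a 21-item scale measuring levels of depression, anxiety and stress over the past week". Section 2.6 gives only the overall age range of 12 to 25. No age quota or expected split appears anywhere.

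Section 2.4 lists these outcomes as secondary endpoints and asks for change at post-intervention and at 6 months, whereas section 2.9 names d only for the pre-post comparison.

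**The concern.** Cohen's d divides a mean change by an estimated standard deviation. In a small sample the reciprocal of that estimate is on average too large, so d lies on average further from zero than the true standardised change. The bias grows as n falls and is therefore largest for RCADS and DASS-21, which share the sample between them.

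For paired data the term Cohen's d also covers several statistics. The mean change can be divided by the baseline SD, the SD of change, or an average of the pre and post SDs. The same data then give different values, and under the present wording the choice could be made after the data are seen or could differ between outcomes.

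What is at stake is how the exploratory findings read. Section 2.9 plans no hypothesis test, so percentage change and d carry the quantitative statement about possible effects. Section 1 cites a "medium-to-large effect size (d = 0.65-0.75") from the proof-of-concept study, and readers are likely to set the new values beside it.

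**Working it through.** **Inputs.** From section 2.9: 15 completers, 25% attrition, 20 enrolled. From section 2.8: RCADS for ages 12-17 and DASS-21 for ages 18-25. From section 1: d = 0.65, the lower prior value, used only to illustrate scale because it compares two groups. Assumed, not in the documents: n per mood scale (10 is half of 20; 7 is about half of 15), pre-post correlation r from 0.3 to 0.8, and normal data.

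**The plan's own figure.** 15 / (1 - 0.25) = 20, which reproduces the enrolment target. The plan contains no power calculation to check. If the target is met, n for the pre-post comparison lies between 15 and 20.

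**Small-sample bias.** With a baseline-SD or change-SD denominator, df = n - 1. The correction factor is J(df) = Γ(df/2) / [√(df/2) · Γ((df-1)/2)]. Plain d has expectation true d / J, so the inflation is 1/J - 1. Hedges' g = J × d, so the reported value falls by 1 - J.

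| n | J(n-1) | Inflation of d | Reduction on correcting | Mean d if the true value is 0.65 | g if d = 0.65 is observed |
|---|---|---|---|---|---|
| 20 | 0.9599 | 4.2% | 4.0% | 0.677 | 0.624 |
| 15 | 0.9453 | 5.8% | 5.5% | 0.688 | 0.614 |
| 10 | 0.9139 | 9.4% | 8.6% | 0.711 | 0.594 |
| 7 | 0.8686 | 15.1% | 13.1% | 0.748 | 0.565 |

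A simulation of 200,000 paired samples with a true baseline-SD d of 0.65 and r = 0.3, 0.5 and 0.8 gave mean values of 0.687 to 0.689 at n=15 and 0.746 to 0.752 at n=7, in line with the formula. With an averaged pre/post SD the means were 0.671 to 0.680 at n=15 (3.2% to 4.6% inflation) and 0.701 to 0.724 at n=7 (7.8% to 11.4%), so the bias is smaller for that version.

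**Bias against random error.** For a true change-SD d of 0.65:
- n=15: bias 0.038, sampling SD 0.313, ratio 0.12.
- n=7: bias 0.098, sampling SD 0.537, ratio 0.18.

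For the baseline-SD version the simulated sampling SD depends on r. It was 0.227 to 0.359 at n=15 and 0.400 to 0.614 at n=7, giving ratios of 0.11 to 0.17 and 0.16 to 0.25.

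The 95% interval (noncentral t) around an observed change-SD d of 0.65 is 0.08 to 1.20 at n=15 and -0.19 to 1.45 at n=7.

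**Denominator.** With equal pre and post SDs, change-SD d divided by baseline-SD d is 1/√(2(1 - r)).

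| r (assumed) | Ratio | Baseline-SD d of 0.65 becomes |
|---|---|---|
| 0.3 | 0.85 | 0.55 |
| 0.5 | 1.00 | 0.65 |
| 0.7 | 1.29 | 0.84 |
| 0.8 | 1.58 | 1.03 |

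The choice lowers d when r is below 0.5 and raises it when r is above 0.5. Over this range it can move d by more than the small-sample bias does.

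**The case against.** The strongest reply is that little depends on these values. The study is a descriptive case series whose primary objectives are feasibility, acceptability and safety. Changes in outcome are only explored, and no test, threshold or decision uses d. Means and SDs are planned for every measure, and the correction depends only on n, so a reader given n can apply it. The bias is also a fraction of the random error. All of this stands, and it is why the point is minor.

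The plan does not say that d will be uncorrected; that is inferred from silence. It is still the natural reading, since the corrected statistic has its own name and section 2.9 does not use it. Preferring the baseline SD to the change SD is a legitimate choice, not the repair of an error. What needs settling is that one denominator is named.

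Three stronger readings are tempting, and the documents do not support them:
- A reader might infer that the planned effects are overstated throughout. Only the small-sample bias has a fixed direction; the open denominator does not.
- A reader might take 7 or 8 participants per mood scale as given. That is an even split of 15, which no section states. An even split of 20 gives 10; a 5/10 split of 15 would give about 25% inflation in the smaller group.
- A reader might infer that a later efficacy trial would be planned 11% to 25% too small (1 - J² at n=15 and n=7). Section 1 says only that more adaptation and development is needed "before its efficacy can be tested in a randomised controlled trial". No section says these values will size that trial, and a single-group pre-post d is not a between-group effect.

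**Conclusion.** The point holds as a minor one. Plain Cohen's d at the planned sample size is biased away from zero by 4.2% to 5.8% for outcomes collected from everyone (n=20 to 15). For RCADS or DASS-21 it is 9.4% at n=10 and 15.1% at n=7, both assumed sizes. These figures rest on normal data and a baseline-SD or change-SD denominator, and are lower with an averaged SD.

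The unnamed denominator is a gap in the specification with no fixed direction: a ratio of 0.85 to 1.58 for assumed r of 0.3 to 0.8 and equal SDs. The absence of an interval matters more to the reader than the absence of the correction. No primary endpoint or study conclusion changes.

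**What to change.** In section 2.9, replace Cohen's d with Hedges' g and state:
- One denominator, named before the data are seen and used for all outcomes, for example the baseline SD of participants who have both values, with the small-sample factor for n - 1 degrees of freedom.
- The n and a 95% confidence interval beside each value, at post-intervention and at 6 months. The interval method should match the denominator; the noncentral t interval shown above is exact only for the change-SD version.
- RCADS and DASS-21 reported separately, each with its own n.
- For the self-harm frequency count, main reliance on the medians and interquartile ranges already planned, because the correction assumes normality, which is doubtful for such counts.

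The cost is a few sentences in the plan, one multiplication per value and the interval calculation; no new data are needed. The downside for the team is that stated effects become about 4% (n=20) to 13% (n=7) smaller.
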